3.2.7 Study procedures

Medical Adhesive Use: During Activa PC+S implantation surgery, a small amount of medical adhesive (Medtronic Part #080118, Dow Corning Medical Adhesive) is placed on the Activa PC+S Implantable Neurostimulator (INS) (Model 37604) header setscrew grommets and the header bore where the lead extensions are inserted and secured. For further information regarding use of medical adhesive during Activa PC+S implantation and replacement please see **Appendix K** (PDF Page 179), **Appendix L** (PDF Page 181) and **Appendix M** (PDF Page 190).

Nexus E Firmware Update: Subjects enrolled in study 2 will sign an updated informed consent, please see **Appendix N** (PDF Page 197) and undergo a Nexus E Firmware update at their next study visits. Subjects who have not yet been implanted with Activa PC+S will undergo Nexus E Firmware update at their initial programming visit. The Nexus E firmware update will take approximately 30 minutes to perform. During the firmware update the

subject will not receive any therapeutic stimulation. For further information regarding Nexus E please see **Appendix E** (PDF Page 120) and **Appendix F** (PDF Page 150.)

SA1: Determine the efficiency and effectiveness on PD signs of aDBS, triggered by patient-specific resting state or movement neural activity, compared to cDBS, using the UPDRS III and validated, high-resolution kinematic metrics of tremor, bradykinesia and freezing of gait (FOG).

SA2: Determine whether aDBS using a kinematic classifier pertinent to the patient specific phenotype is more efficient and/or effective on PD symptoms than aDBS using the using the patient's specific resting or movement state neural classifier and/or cDBS.

Aim 1 and 2 will be done at the time of initial programming of the DBS system and at the first follow-up visit for subjects who consent before DBS implantation. For subjects who already have the Activa PC+S implanted, Aims 1 and 2 will be performed after they have completed Study 1:

1. Patients will arrive in the off medication, OFF DBS state. Medication will be stopped 72 hours (extended release forms of dopamine agonists), 24 hours (regular form of dopamine agonists, controlled release forms of carbidopa/levodopa (CD/LD)) and/or 12 hours (regular CD/LD, entacapone, rasagiline, selegiline, amantadine) before testing. The DBS system will not have been activated after implantation or will be turned off as per the protocol in Study 1.
2. An interval history, examination, and UPDRS III will be performed. LFPs will be recorded from the DBS leads at rest during the repetitive wrist flexion-extension task and during stepping in place.
3. Real-time STN LFP beta band power will be calculated both OFF DBS and during “therapeutic” DBS. DBS will be applied through the electrode (1 or 2) that lies in between the electrode pair (0-2 or 1-3) with the greatest beta power. Therapeutic DBS: 140 Hz, 60 microsec at 3 volts OR the highest voltage <3V, that does not cause adverse effects.
4. We will determine if the therapeutic DBS will attenuate rest beta power by $\geq 40\%$ ⁴.
5. Patients will be seated at rest, or while performing self-paced repetitive wrist flexion-extension (WFE) for periods of 10 seconds after a “Go” signal with angular velocity sensors attached to the hand.
6. **SA1a and SA2a (Initial Programming or Initial visit):** Determination of classifier thresholds: 1. Resting or movement state neural: ON and OFF triggers when the beta band power is greater than or less than different thresholds of the resting or movement state beta power differential (beta power OFF – ON therapeutic DBS). 2. Kinematic (tremor/bradykinesia): ON and OFF triggers when rectified tremor amplitude/root mean square angular velocity (Vrms) of WFE is greater than or less than different thresholds of tremor/Vrms differential (OFF – ON therapeutic DBS) respectively. **SA1b and SA2b (First Followup Visit):** Outcomes will be measured after 30 minutes of aDBS or cDBS. For neural and tremor aDBS, the Activa® PC+S will be updated in real time (see delays). For bradykinesia aDBS, the Activa® PC+S will be updated with the Vrms from 10 second epochs of WFE that the PD subject will perform every 2 minutes during the 30 minute trial (rwFE, angular velocity sensors, Motus Motion analysis system, and EMG). **SA3:** Determine whether aDBS is more efficient and effective than cDBS in the optimized on medication state after six months of cDBS.

Aim 3 will be completed after 6 months of continuous DBS and optimized therapeutic medication.

7. Patient arrives in on medication/on stimulation state. Patient is instructed to bring appropriate doses of medication to take throughout the day at pre-set intervals.
8. An interval history, examination, and UPDRS III will be performed. LFPs will be recorded from the DBS leads during some of the clinical assessments such as the repetitive wrist flexion-extension task and during stepping in place.
9. Real-time STN LFP beta band power will be calculated both on medication/OFF DBS, and during “therapeutic” DBS. DBS will be applied through the electrode (1 or 2) that lies in between the electrode pair (0-2 or 1-3) with the greatest beta power. Therapeutic DBS: 140 Hz, 60 microsec at 3 volts OR the highest voltage <3V that does not cause adverse effects.
10. We will confirm that the therapeutic DBS will attenuate rest beta power by $\geq 40\%$ ⁴.
11. Patients will be seated at rest, or while performing self-paced repetitive wrist flexion-extension (WFE) for periods of 10 seconds, after a “Go” signal with angular velocity sensors attached to the hand.
12. SA3: Determination of classifier thresholds: 1. Resting or movement state neural: ON and OFF triggers when the LFP band power or variability is greater than or less than different thresholds of the resting or movement state LFP power differential (LFP power OFF – ON therapeutic DBS). 2. Kinematic (tremor/bradykinesia): ON and OFF triggers when rectified tremor amplitude/root mean square angular velocity (Vrms) of WFE is greater than or less than different thresholds of tremor/Vrms differential (OFF – ON therapeutic DBS) respectively.
13. Outcomes will be measured during trials up to 8 hours of aDBS or cDBS. For neural and tremor aDBS, the Activa® PC+S will be updated in real time (see delays). For bradykinesia aDBS, the Activa® PC+S will be updated with the Vrms from 10-60 second epochs of WFE that the PD subject will perform throughout during the trial (rwFE, angular velocity sensors, Motus Motion analysis system, and EMG).

Blinding: The PD subject, investigators (certified) performing the UPDRS III, and investigator analyzing data will be blinded to the type of DBS used for a particular experiment. All experiments will be videotaped and two additional independent certified raters will rate the UPDRS III.

Randomization: The order of aDBS, cDBS, and all motor tasks will be randomized for each subject and enough time will be given in between for patient rest and for return to baseline of beta power, tremor, and bradykinesia.

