3.2.2 Specific Aims

SA1: Determine the efficiency and effectiveness on PD signs of aDBS, triggered by patient-specific resting or movement state neural activity, compared to cDBS, using the UPDRS III and validated high-resolution kinematic metrics of tremor, bradykinesia and freezing of gait (FOG).

Primary Hypothesis: Resting state aDBS will reduce energy consumption compared to cDBS as well as improve overall motor outcome, but may have differing effects on the individual PD motor signs.

SA1a. Determine the neural classifier of the resting or movement state to use as a trigger for aDBS. Hypothesis: Patient-specific beta band synchrony is a classifier of the off therapy resting or movement state in PD and can be used as a trigger for aDBS^{1,2}. Using individualized algorithms, resting or movement state neural activity will be tested as the stimulation trigger, activating aDBS when beta power is above a specific threshold. SA1b. Compare the efficiency and effectiveness on PD symptoms of aDBS (using the patient specific resting state neural classifier) compared to cDBS at the same neurostimulation parameters.

SA2: Determine whether aDBS using a kinematic classifier pertinent to the patientspecific phenotype is more efficient and/or effective on PD symptoms than aDBS using the using the patient’s specific resting or movement state neural classifier and/or cDBS.

Secondary Hypothesis: Different PD motor phenotypes may respond better to aDBS triggered by the kinematic classifier respective to that state than to aDBS triggered by the resting or movement state neural classifier or to cDBS.

SA2a. Determine the kinematic classifiers for the states of tremor and bradykinesia, and develop the control policy algorithms of optimal DBS settings that improve each motor abnormality. SA2b. Compare the efficiency and effectiveness on PD symptoms of tremor or bradykinesia kinematic aDBS versus resting or movement state neural aDBS and cDBS.

SA3: Determine whether aDBS is more efficient and effective than cDBS in the optimized on medication state after six months of cDBS.

Tertiary Hypothesis: Neural and/or kinematic classifiers and control policy algorithms will need to be adapted to different medication states, making aDBS more or less useful. After six months of cDBS plus medication, SA1 and SA2 will be repeated in the optimized on medication state. The control policy algorithms will be adjusted as necessary to adapt to this state.

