3.2.10 Data Analysis

Experimental outcomes: Beta power, UPDRS III and quantitative measures of tremor (rest tremor recording for 1 minute), bradykinesia (WFE task) and FOG (using a Stepping in Place (SIP) task and gait analysis), and time DBS ON over the 30 minutes on aDBS.

Number of arms: (One) Patients will be used as their own controls.

All quantitative data will be post-processed using custom MATLAB software (The MathWorks, USA).

1. **Repetitive wrist flexion-extension movement – rwFE:** The Motus motion analysis system will be used to obtain an objective quantitative assessment of bradykinesia by measuring hand angular velocity during a quantitative repetitive wrist flexion-extension task (rwFE). The system consists of sensors in which vibrating quartz crystals act like solid-state gyroscopes and produce an analog signal whose voltage is proportional to the angular velocity when rotated about its measurement axis. These sensors are unlike conventional accelerometers in that they are indifferent to their orientation with respect to gravity. Each sensor weighs about 60 g, has a maximum range of 1,900 degrees per second, a low noise level of 1 degree per second RMS, and a flat response to 30 Hz. The angular velocity data will be digitized at a rate of 100 samples per second per sensor. The root mean square velocity of angular movement (Vrms) will be used as an indication of the average speed at which the flexion-extension task is performed. The frequency spectrum of the angular velocity will be analyzed using a fast Fourier transform (FFT) analysis in each trial to ensure that patients' movements are not dominated by a fast-action tremor (7–12 Hz).
2. **Tremorography;** Using the above mentioned angular velocity sensors, the angular velocity data during rest and/or postural poses will be digitized at a rate of 100 samples per second per sensor and the frequency spectrum will be will be analyzed using an FFT analysis to detect and quantify the type of tremor (rest 4-6 Hz or action/postural 712 Hz) that is present.

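### SA2b schedules wrist flexion-extension during the block only for bradykinesia aDBS, so unless the comparator blocks have equal exposure its Vrms contrast cannot separate the trigger from repetition of the outcome task

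*Combined protocol and SAP*

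**What the plan says.** For SA1b and SA2b at the first follow-up visit, section 3.2.7 sets the timing: "Outcomes will be measured after 30 minutes of aDBS or cDBS". It then says how the stimulator is driven in each kind of aDBS.

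- **Neural and tremor aDBS:** "For neural and tremor aDBS, the Activa® PC+S will be updated in real time (see delays").
- **Bradykinesia aDBS:** the device takes Vrms from "10 second epochs of WFE that the PD subject will perform every 2 minutes during the 30 minute trial".
- **cDBS:** no task within the block is stated.

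Step 5 of the same section is more general: "Patients will be seated at rest, or while performing self-paced repetitive wrist flexion-extension (WFE) for periods of 10 seconds". It names no stimulation condition and sets no repetition schedule.

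Section 3.2.10 lists the WFE task as the bradykinesia measure and uses Vrms as its index of speed. The contrast at issue is SA2b in section 3.2.2: "Compare the efficiency and effectiveness on PD symptoms of tremor or bradykinesia kinematic aDBS versus resting or movement state neural aDBS and cDBS".

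Three other provisions bear on this. The randomization paragraph of 3.2.7 randomizes the order of conditions and motor tasks, with rest of unspecified length between them. The note in 3.2.8 gives every subject practice trials. Step 13 of 3.2.7 (SA3) again mentions WFE epochs, of 10 to 60 seconds, only for bradykinesia aDBS, in trials of up to 8 hours.

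**The concern.** The task that feeds the bradykinesia trigger is also the task on which bradykinesia is scored. Followed as written, the patient repeats it at regular intervals up to the outcome measurement in one condition, while nothing comparable is prescribed in the conditions it is compared with. A Vrms difference could then come from the trigger, or from having just performed the task many times. Warm-up or practice would raise Vrms and fatigue would lower it, so the direction of any bias cannot be predicted.

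Vrms is the outcome closest to the sign that this trigger targets, so it is the natural measure for this SA2b comparison. A larger sample would not help, because the repetition belongs to the condition. Exposure that is neither controlled nor recorded during testing cannot be recovered in the analysis.

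**Working it through.** The plan states no figure for in-block exposure, so there is none to reproduce. The count below uses section 3.2.7.

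**Inputs:** block 30 min = 1800 s; epoch 10 s; one epoch every 2 min.

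**1. Prescribed exposure, bradykinesia aDBS.** 30 / 2 = 15 epochs; 15 × 10 s = 150 s; 150 / 1800 = 8.3% of the block. If neither minute 0 nor minute 30 counts: 14 epochs, 140 s, 7.8%. If both count: 16 epochs, 160 s, 8.9%.

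**2. Imbalance against a comparator block.** Comparator exposure is not stated, so let it be k epochs (an assumption). Imbalance = (15 − k) × 10 s.

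| k assumed | Imbalance | Share of block |
|---|---|---|
| 0 | 150 s | 8.3% |
| 5 | 100 s | 5.6% |
| 10 | 50 s | 2.8% |
| 15 | 0 s | 0% |

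This measures exposure, not bias in Vrms. The documents give no repetition effect from which bias could be computed.

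**3. Do the plan's safeguards remove the imbalance?**
- *Random order* balances period effects. The epochs go with the bradykinesia condition wherever it falls in the order.
- *Rest between* may or may not cover the gap before the outcome WFE. No lag after the last epoch is given.
- *Practice trials* make new learning less likely. They do not address warm-up or fatigue within a block.
- *Step 5* neither establishes nor excludes equal exposure.

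**4. SA3.** Epoch length is given as a range and no interval is stated, so exposure cannot be counted. The one-sided description is the same.

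**5. Cost of matching.** Suppose epochs are added to an aDBS comparator block and each disturbs the trigger for its own 10 s plus an assumed further g seconds. The largest possible change in time DBS ON is 15 × (10 + g) / 1800.

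| g assumed | Time affected | Largest change | Block left undisturbed |
|---|---|---|---|
| 0 s | 150 s | 8.3 points | 1650 s = 27.5 min |
| 10 s | 300 s | 16.7 points | 1500 s = 25 min |
| 20 s | 450 s | 25 points | 1350 s = 22.5 min |

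With matched epochs, the imbalance in step 2 becomes 0 s.

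**The case against.** **The asymmetry is read from silence.** The sentence on bradykinesia aDBS says where the controller's input comes from; it is not a task schedule for every block. Step 5 uses the same 10-second length without naming a condition, and a movement-state neural trigger presupposes some movement. This stands in part. A reader might infer that comparator patients do no WFE at all, but the documents do not support that: their exposure is unstated, not zero. It remains true that the only written schedule belongs to one condition.

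**The epochs are part of the strategy.** A Vrms trigger cannot run without movement, so comparing trigger plus task with cDBS is legitimate. This stands. What is lost is attribution to the trigger alone. SA2 frames its question around the classifier, so readers are likely to draw that conclusion.

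**Fatigue is unlikely.** Each 10 s epoch is followed by 110 s without one, a ratio of 11 to 1, and the outcome WFE need not come first among the randomized tasks. This makes fatigue less likely, but does not exclude it and says nothing about warm-up.

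**The effect may be negligible.** Take 27 pairs, two-sided alpha 0.001, and the plan's ON-versus-OFF SD of 63 points for Vrms. With no trigger effect, assumed repetition shifts of 5, 10 and 20 points would give rejection rates of 0.19%, 0.55% and 3.6%. With an assumed SD of 20 they would be 1.7%, 17% and 91%. Neither SD is known to apply to an aDBS-versus-comparator difference, and the shifts are invented. The calculation shows only that the size is undetermined.

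**Matching could harm the primary hypothesis**, which reads "Resting state aDBS will reduce energy consumption compared to cDBS as well as improve overall motor outcome". Movement added to resting-state blocks could change "time DBS ON over the 30 minutes on aDBS". This stands, and the fix leaves those blocks alone.

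**Conclusion.** The point holds in conditional form. Section 3.2.7 prescribes about 150 s of the outcome task (8.3% of the block) in bradykinesia aDBS and states none for its SA2b comparators. Unless exposure is in fact equal, the Vrms contrast cannot separate the trigger from task repetition. This is more than a missing detail, because the plan's own schedule places the repetition in one condition and its safeguards do not remove it.

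The scope is limited to WFE Vrms in contrasts that involve bradykinesia aDBS, under a secondary aim of an open-label pilot. SA1b and outcomes not based on WFE (rest tremor, stepping in place, gait) are not directly affected. SA3 is affected only so far as WFE exposure differs between its trials.

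Two stronger readings are tempting, and the documents support neither. A reader might infer that the distinctive schedule breaks the patient's blind, but nothing says that patients know which DBS type the schedule goes with. A reader might also express a repetition effect as a share of the plan's 45% Vrms change, but that figure compares ON with OFF DBS, and no repetition effect is given to set against it.

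**What to change.** First state the WFE exposure of every block. If it is already equal, with the same lag to the outcome task, that sentence settles the matter. If not:

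1. Where the comparator is movement-state neural aDBS with its paired cDBS block, cue the same 10-second epochs every 2 minutes in both. Let Vrms drive stimulation only in the bradykinesia condition.
2. Take the outcome WFE at the same fixed lag after the end of every block, following the last epoch where epochs are run.
3. Keep resting-state neural blocks and their paired cDBS blocks free of movement. This protects the resting-state energy hypothesis and keeps SA1b, which is "compared to cDBS at the same neurostimulation parameters", balanced. Report their Vrms comparison with bradykinesia aDBS as one of whole strategies (trigger plus task), not of the trigger alone.
4. Apply the same rules in SA3.

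**Cost.** These are changes to procedure wording, with no extra visit or staff. The downside is about 8% movement time in the matched comparator blocks, which may alter beta power and time DBS ON. Flag the epochs and report both measures with and without them; this shows the disturbance but does not undo it. The plan does not say how many cDBS blocks each patient has. If one cDBS block has to serve both neural triggers, it cannot be both matched and movement-free. The sponsor would then add a 30-minute cDBS block, or keep the single block movement-free and report its Vrms comparisons with any block that contains epochs as whole strategies.

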3.2.8 Clinical Assessments

Clinical Assessments	Pre-surgery Baseline	Initial programming	1 mo. Post IP	6 mo. post IP
	Off Meds	Off Meds	Off Meds	On Meds
Repetitive Wrist Flexion-Extension Movement	x	x	x	x
Tremorography	x	x	x	x
Stepping in Place (SIP)	x	x	x	x

Gait Analysis		x	x	x
UPDRS III / H&Y	x	x	x	x
Medical History	x	x	x	x
Physical Exam	x			
MOCA	x			
Columbia Suicide Severity Scale	x	x	x	x
Electromyography (EMG)		x	x	x
Local Field Potentials		x	x	x
Adaptive DBS Testing (Kinematic and Neural triggers)			x	x

Note: The subjects will be given practice trials for all of the quantitative tasks listed below to ensure that the goal and the instructions of the task are understood before each assessment is performed. At the baseline visit, the baseline version of the Columbia Suicide Severity scale (CSSS) will be used. At every subsequent visit, the “Since last visit” version of the CSSS will be used.

1. **Repetitive wrist flexion-extension movement – rwFE:** Using solid-state gyroscopic sensors (Motus Motion analysis system) that fit like a glove on the patient's hands and surface EMG sensors (Delsys Bagnoli 2 EMG System) placed on the wrist flexor and extensor muscles, the wrist movement and the muscle activation patterns will be quantified. Specifically, we will directly measure angular velocity and muscle activations. The patient's arm will be kept at 90 degrees in elbow flexion with the forearm in a neutral position. The patient will perform a wrist flexion-extension movement continuously from the “go” to the “stop” command. This test will assess the subject's bradykinesia state.
2. **Tremorography:** If the subject shows visible tremor of the hands using the above mentioned angular velocity sensors, his/her resting or postural tremor behavior will be measured. Surface EMG sensors will be placed on forearm muscles to capture the muscles' activation pattern.
3. **Repetitive alternating finger tapping (RAFT) keyboard task:** RAFT is a computerized objective measure of movement velocity, speed of movement, and timing using an engineered keyboard (Quantitative DigiGraphy) with two adjacent keys. The subject will alternatively finger tap (trill) on the keyboard. The test will be performed twice for each hand. The patient will be seated at a table on which the keyboard is placed with the hand that does not perform the task placed in his/her lap. The subject will be instructed to tap as fast as s/he can while maintaining the alternating movement. This test will quantify a set of movement abnormalities seen in Parkinson's disease patients such as bradykinesia, freezing of movement, tremor, or fatigue.

4. **Stepping in place (SIP) task:** The subject will be asked to step in place repetitively on two adjacent force plates (Smart EquiTest, Neurocom Inc) with each foot on each forceplate. The subject will step at a speed similar to his/her normal walking. A baseline quiet stance will be acquired at the beginning and the end of the test. The subject will wear a harness to protect him/her from falling. This test will quantify measures such as gait asymmetry, gait rhythmicity, and left-right step coordination. These metrics may provide clues to underlying mechanisms involved in freezing of movement in PD. Our lab showed that the SIP metric has a high sensitivity (93%) and specificity (87%) for identifying freezers from non-freezers⁵.
5. **Unified Parkinson's Disease Rating Scale part III – Motor Examination (UPDRS III):** The clinical motor assessment of the subject will be performed using the UPDRS III scale.
6. **Gait Analysis:** Subjects will wear sensors on their hands, arms, chest, trunk, feet and legs (Opal sensors, APDM, Inc). These tasks will quantify measures such as gait asymmetry, gait rhythmicity and left-right step coordination during subjects normal walking. Subjects may be asked to do regular forward walking as well as walking around obstacles (such as chairs, or small room dividers) **or turning in place**. These obstacles **and turning in place** will be used in order to elicit freezing, which often occurs in constrained spaces. This type of freezing is frequently encountered in subjects' daily lives. Subjects will be monitored carefully by research team in order to ensure their safety and comfort.
7. **Cognitive Testing:** Subjects will be administered the Montreal Cognitive Assessment at visits after the pre-surgery baseline visit. In both the resting and movement state, subjects will perform cognitive tasks that include but are not limited to reciting the months of the year backwards and serial 7s.
8. **Speech Assessment:** While wearing a voice-recording headset, subjects will be performing speech tasks that include reading sentences and phonation.
9. **Vibrotactile Stimulation:** Subjects may be asked to perform the above gait tasks with sensory cueing using the VibroGait system. Intermittent vibrotactile stimulation may be applied to the wrists, or another body part with intact sensation, in a manner that is either coordinated with or unrelated to the subject's gait cycle in real time. Subjects will be allowed to practice with the VibroGait on before completing the tasks.

In addition to Nexus testing, subjects attending clinical programming follow-up visits will come in off medication and on stimulation and will be asked to repeat quantitative assessment of motor function and simultaneous LFP recording. Subjects come in for programming visits every 3-6 months for 1-3 years post device implantation. Patients who receive replacement Activa PC+S devices will continue to complete the same assessments listed above in order to further the aims of both Study 1 and 2. These experiments will allow us to collect data related to longer term disease tracking. Disease tracking includes monitoring the patients' beta band over time, in accordance with SA3 from study 1 (SA3: Determine the long-term effects of STN DBS on neural signatures and motor behavior; ascertaining whether long-term DBS changes the underlying neural signatures and dose response characteristics of PD behavioral states).

Testing for disease tracking will include quantitative digitography (QDG), quantitative range of motion analysis (Motus, LG G Watch, APDM System), tremorography, surface electromyography (EMG), and computerized dynamic posturography, SIP, gait analysis, cognitive testing and UPDRS III. Testing for replacement device patients will also include aDBS experiments, with the same protocol as detailed above. The subjects will perform these

assessments in the on clinical stimulation state and will repeat all or a subset of these tests in the off stimulation state.

